	
 
within 2 weeks prior to Day 1 of treatment in the study.
 
Tesevatinib is largely metabolized by CYP3A4. Therefore, taking any medication known to strongly inhibit the CYP3A4 isozyme or any drugs that are strong CYP3A4 inducers (including anti-epileptic agents such as phenytoin). A stable regimen (≥ 4 weeks) of antidepressants of the SSRI class is allowed (common SSRIs include escitalopram oxalate, citalopram, fluvoxamine, paroxetine, sertraline, and fluoxetine). See Appendix 4.
 
Steroid medications are allowed
 
				
	• Radiation therapy: need for radiation will be considered to be progressive disease				
Safety assessments	The National Cancer Institute Common Terminology Criteria for Adverse Events (NCI CTCAE; Version 4.03) will be used for grading toxicities. Safety assessments will include AEs, serious adverse events (SAEs), PEs including full neurologic exam, vital sign measurements, clinical safety laboratory evaluations (hematology, serum chemistry and urinalysis) KPS and ECGs				
	The AE reporting period for a patient enrolled in the study begins when the patient provides informed consent and is continued through 30 days after the last dose of study drug or until start of new treatment. All AEs that occur in enrolled patients during the AE reporting period specified in the protocol must be recorded, regardless of the relationship of the AE to study drug. Any known untoward event that occurs beyond the AE reporting period that the investigator assesses as at least possibly related to tesevatinib should be reported to Kadmon.				
	Vital sign measurements, including sitting blood pressure, pulse rate, respiratory rate, and temperature will be monitored throughout the study.				
Plasma Concentration Evaluation of Tesevatinib	Plasma samples for tesevatinib concentration analysis will be drawn predose of tesevatinib on Days 15 of Cycle 1; and predose of tesevatinib on Day 1 of every subsequent cycle (up to cycle 6). Data from these samples will contribute to a population PK analysis, and will be used to explore exposure-response relationships.				
Pharmacodynamic Evaluation	Samples will be evaluated for the EGFRvIII mutation and for EGFR gene amplification.				
Efficacy	Disease assessments will be based on the RANO criteria [Wen 2010] and will comprise radiological assessments, clinical assessments, and corticosteroid use (see Appendix 2). Per the study's schedule of assessments, full disease assessments				

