#### **Overall Disease Assessment**

Based on radiological assessments, clinical status, and corticosteroid use, an overall evaluation of CR, PR, stable disease (SD), or progressive disease (PD) should be made at each disease assessment after baseline according to the RANO criteria (Appendix 2). Progressive disease is defined as any of the following:

- ≥ 25% increase in sum of the products of perpendicular diameters of enhancing lesions (compared with baseline if no decrease or otherwise compared with the smallest recorded sum [nadir] during the study) on stable or increasing doses of corticosteroids
- Significant increase in T2/FLAIR non-enhancing lesions on stable or increasing doses or corticosteroids (compared with baseline or best response after initiation of therapy)
- Appearance of any new lesions
- Clear progression of nonmeasurable lesions
- Definite clinical deterioration not attributable to other causes apart from the tumor, or to decrease in corticosteroid dose

Failure to return for evaluation as a result of death or deteriorating condition
 Note: Increase in corticosteroid dose alone, in the absence of persistent clinical
 deterioration related to tumor, will not be used as a determinant of progression. Patients
 whose corticosteroid dose was increased for new symptoms and signs without
 confirmation of disease progression on neuroimaging do not qualify for disease
 progression and should continue study treatment. If subsequent follow-up imaging
 shows that this increase in corticosteroids was required because of disease progression,
 the date of progression should be the first timepoint at which the increase in

	corticosteroids was necessary.
Patient Reported	Patient reported outcomes (PROs) of disease- and treatment-related symptom severity
Outcomes and Mini-	and symptom interference will be assessed using the MDASI-BT questionnaire.
Mental State	
Examination	The MDASI is a validated and reliable self-report measure that was developed to assess
	symptom sevently and interference [Cleeland 2000; Armstrong 2006].

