### 9.3.2. Additional Anti-Cancer Treatment and Radiotherapy

Patients should not receive additional therapeutic anti-cancer treatment until after PD has been documented on study and End of Treatment study assessments have been completed. If a patient requires additional anti-cancer treatment, study treatment will be discontinued and the patient will enter the Post-Treatment Period and followed every 8 weeks by phone call.

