#### 12.2.14. Follow-up Phone Contact

Beginning 8 weeks after the 30-Day Follow-Up Visit, patients are to be contacted by telephone every 8 weeks to assess survival status and any subsequent anti-cancer treatment. If PD was not observed before the 30-day follow-up period patients will need to return for follow-up MRI until PD is demonstrated or they start a new anti-cancer treatment. In the case of a patient receiving a new anti-cancer treatment in the absence of PD, the date of the most recent MRI will be used as the date of PD.

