## 13.4.6. Efficacy/Activity

## **13.4.6.1.** Primary efficacy endpoint

## Progression-Free Survival at 6 months (PFS-6).

PFS is defined as the time between date of first dose and the date of first documented disease progression or death, whichever occurs first. The PFS-6 is defined as a patient being alive and progression free at 6 months (24 weeks). Disease progression will be determined based on investigator assessment with use of radiological assessments, clinical status, and corticosteroid

use. The specific criteria for disease progression is defined in Appendix 2. Patients without a date of disease progression or death will be analyzed as censored observations on the date of the last disease assessment; if no post-baseline disease assessment is available, PFS will be censored at the date of 1st dose.

The analysis of the primary endpoint and the estimation of PFS-6 is performed with a Cox model. Karnofsky performance status is included as a covariate. Study center is included as a random effect assumed to follow a gamma distribution. Thus, this is a shared Cox gamma frailty model. The model is used to estimate PFS-6 with 2-sided 95% and 90% confidence intervals.

Furthermore, Kaplan-Meier methodology will be used to estimate median PFS with 95% CI and the Kaplan-Meier curve will be constructed to provide a visual description of the PFS over time.

Descriptive statistics overall and for each parameter (radiological assessment, clinical status and corticosteroid dose) in the disease progression assessment are presented for the entire assessment period as well as for 3, 6 and 9-month time points.

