Progression (PD)	
 
Defined by any of the following:
 
≥25% increase in sum of the products of perpendicular diameters of enhancing lesions compared with the smallest tumor measurement obtained either at baseline (of no decrease) or best response, on a stable or increasing dose of corticosteroids
 
Significant increase in T2/FLAIR non-enhancing lesions on stable or increasing doses of steroids compared with baseline scan or best response after initiation of therapy, not caused by comorbid events (e.g., radiation therapy, demyelination, ischemic injury, seizures, postoperative changes, or other treatment effects)
 
Presence of any new lesions
 
Clear clinical deterioration not attributable to other causes apart from the tumor (e.g., seizures, medication adverse effects, complications of therapy, cerebrovascular events, infection, and so on) or decreases in corticosteroid dose
 
Failure to return for evaluation due to death or deteriorating condition
 
Clear progression of nonmeasurable disease
 

FLAIR = fluid-attenuated inversion recovery, RANO = Response Assessment in Neuro-Oncology (adapted from Wen 2010)

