#### 3.1.4.3 Progression-Free Survival (PFS) Endpoints

PFS is defined as the time from date of first dose to the date of disease progression or death, whichever happens first. For subjects who do not have an event (i.e. those who have not progressed, and are alive at the date of data cut-off or lost to follow-up), progression-free survival will be censored on that date.

PFS will be summarized using Kaplan-Meier methods for 25th percentile, median, and 75th percentile. 95% Confidence intervals will be calculated using Greenwood Formulation. Kaplan-Meier curves will be plotted for populations in the analysis.

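### Protocol rules that count need for radiation, or new anti-cancer treatment without PD, as progression are absent from the endpoint criteria and the SAP; the main exposure is PFS, median PFS and DOR

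*Protocol*

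**What the plan says.** **Text that makes it an event**
- Protocol synopsis, Prohibited treatments: "need for radiation will be considered to be progressive disease". The trigger is need, and no date is given.
- Protocol 12.2.14: for "a patient receiving a new anti-cancer treatment in the absence of PD, the date of the most recent MRI will be used as" the PD date. A Table 1 footnote on long-term follow-up repeats the rule. The trigger is receipt of any new anti-cancer treatment, and the date is that of an earlier scan.

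**Text that does not**
- Protocol 13.4.6.1, on the primary endpoint: "The specific criteria for disease progression is defined in Appendix 2". Appendix 2 lists six PD items: enhancing lesions, T2/FLAIR lesions, new lesions, clinical deterioration, nonmeasurable disease, and "Failure to return for evaluation due to death or deteriorating condition". Radiation and new treatment are not among them.
- The synopsis's own list, introduced by "Progressive disease is defined as any of the following", has neither item.
- Protocol 9.3.2: "If a patient requires additional anti-cancer treatment, study treatment will be discontinued and the patient will enter the Post-Treatment Period". This is not called PD.
- SAP 3.1.4.3 counts progression or death only. SAP 3.8.1 points to RANO in Appendix 2. Neither mentions radiation or new treatment.

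**Censoring and follow-up**
- Protocol 13.4.6.1 censors patients without an event at the last disease assessment.
- SAP 3.1.4.3 refers to patients without an event at data cut-off or lost to follow-up, and says "progression-free survival will be censored on that date".
- SAP 3.8.1 counts unknown week-24 status as not progression-free.
- Protocol 12.2.14 and the Table 1 footnote end follow-up MRIs at PD or new treatment. Protocol Sections 10 and 12.1.10 continue assessments until progression.
- The synopsis says long-term follow-up is not required from Amendment 4 on.

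**The concern.** A patient who starts radiation or another anti-cancer treatment without RANO progression is an event in two places in the protocol. Under the criteria that the endpoint section and the SAP actually use, the same patient is not an event. A programmer following the SAP would drop an event rule that the protocol states. The patient would then be carried to data cut-off or loss to follow-up, beyond the point at which 12.2.14 stops the scans that could show progression.

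Both steps push the PFS curve and median PFS upward. DOR follows, because SAP 3.8.2.5 uses the 3.1.4.3 method. The trial is single-arm and open-label with an investigator-assessed endpoint. An unsettled event rule would therefore be settled after the data are known.

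**Working it through.** **1. The plan's own figures.** These come from Protocol 13.2 and 13.3: N = 40, PFS-6 of 25%, one-sided 5% (lower limit of the 90% interval).
- Treating PFS-6 as binomial(40, 0.25), with log, log-log, logit or Wilson limits, the power is 95.7% against 7% and 81.8% against 10%. The plan states 95% and 80%.
- Agreement depends on the interval. Wald limits give 90.4% and 70.0%. The protocol's own simulation cannot be rerun, because accrual and censoring are not stated.
- Interim: P(at most 1 of 21 | 5%) = 0.95^21 + 21 × 0.05 × 0.95^20 = 71.7%. The plan states 72%.

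The design arithmetic is sound to that extent. The issue is one of definition.

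**2. Patient A.** No RANO PD, last MRI at week 16, radiation needed and started at week 20.

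| Source | PFS result |
|---|---|
| Synopsis | Event, undated (week 20 if dated at need) |
| 12.2.14 and Table 1 footnote | Event at week 16 |
| Appendix 2 with 13.4.6.1 | No event; censored at last assessment (week 16 if no later scan) |
| SAP 3.1.4.3 | No event; censored at data cut-off or loss to follow-up |

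If the synopsis event were dated at need, the two event dates would differ by 20 − 16 = 4 weeks. With scans every 8 weeks after week 8, kept on schedule, that gap can reach about 8 weeks.

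If the SAP date is cut-off at week c for this patient, the unassessed time credited is c − 16 weeks. As assumed values, c = 24 gives 8 weeks and c = 52 gives 36 weeks.

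**3. Patient A and PFS-6.**
- No week-24 scan: status is unknown, so SAP 3.8.1 gives a failure. The synopsis and 12.2.14 give the same result.
- A week-24 scan without PD: success under the SAP, failure under both protocol event rules (with the synopsis event dated at need).

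**4. Patient B.** MRI without PD at week 24, radiation at week 28.
- SAP: success.
- Synopsis, if dated at need: success.
- 12.2.14: PD dated week 24, so arguably a failure.

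**5. Size for PFS-6.** One patient is 1/40 = 2.5 points. The number of such patients is not in the documents, so the table assumes 0 to 3 reclassified from 10/40, with Clopper-Pearson limits (the SAP 3.1.4.2 method).

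| Reclassified | PFS-6 | 95% CI | Lower 90% limit |
|---|---|---|---|
| 0 | 25.0% | 12.7–41.2 | 14.2% |
| 1 | 22.5% | 10.8–38.5 | 12.3% |
| 2 | 20.0% | 9.1–35.7 | 10.4% |
| 3 | 17.5% | 7.3–32.8 | 8.5% |

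One patient, from 8/40 to 7/40, takes the lower 90% limit across the protocol's 10% benchmark. Likewise, 2 of 21 continues at the interim and 1 of 21 stops.

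**The case against.** **PFS-6 is mostly protected.** A reader might infer that every irradiated patient shifts the primary result. The documents do not support that. If scans stop at new treatment, a patient treated before week 24 normally has unknown status and already fails under SAP 3.8.1. This stands, and it confines the PFS-6 effect to the two situations in steps 3 and 4 of the working.

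**The two protocol event rules need not compete.** A reader might see three rival definitions of the primary event. In fact the synopsis and 12.2.14 agree that the irradiated patient has an event. The synopsis gives no date, so an early-versus-late conflict between them requires a date that it never states. This also stands. What remains is a difference in trigger (need versus receipt, radiation versus any new treatment) and the absence of both rules from the endpoint criteria.

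**SAP silence is not denial.** The SAP takes the progression date as given, and an investigator could already have applied the synopsis rule. This stands in part. But 13.4.6.1 names Appendix 2 as the specific criteria, and 9.3.2 does not call such patients progressed, so sites can reasonably differ. SAP 3.1.2 says methods were changed where necessary without listing the changes, so the omission cannot be read as a decision.

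**SAP censoring need not run to cut-off.** SAP 2.2 ends follow-up 30 days after the last dose or at new treatment, so loss to follow-up could be read as that date. This is a possible reading, but 3.1.4.3 does not say so, and it is still not the last disease assessment.

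**Section 12.2.14 may be dormant.** It belongs to long-term follow-up, which is no longer required from Amendment 4 on. This stands as an uncertainty, but the rule remains in the text in two places.

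**The case may be rare.** Radiation is prohibited on study, and 9.3.2 asks that other treatment wait for documented PD. No frequency is available. Even so, 12.2.14 legislates for treatment without PD, so the protocol foresees it.

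**Conclusion.** The point holds as an inconsistency in event definition and censoring. The protocol states event rules for need for radiation and for new treatment without PD. Its named endpoint criteria and the SAP do not contain them, and the SAP's censoring date differs from the protocol's. Followed as written, the SAP can credit unassessed progression-free time to PFS, median PFS and DOR.

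The documents do not support the stronger reading that the primary result as a whole is undefined. PFS-6 moves, by 2.5 points per patient, only where a treated patient still has a week-24 scan without PD or an event date falls near week 24.

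The total effect cannot be derived, because the number of such patients is not given. The 0-to-3 range and the cut-off weeks in the working are assumptions. The point merits correction before analysis, but it does not affect sample size or stated power.

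**What to change.** 1. Reconcile these texts into one endpoint rule giving event status and event date for radiation or new anti-cancer treatment without RANO PD: the synopsis (Prohibited treatments and PD list), the Table 1 footnote, 9.3.2, 12.2.14, 13.4.6.1, Appendix 2, and SAP 3.1.4.3 and 3.8.1.
2. Carry the event status that the protocol already states into SAP 3.1.4.3 and 3.8.1. State one date, use it in both 12.2.14 and the Table 1 footnote, and say whether that rule still applies after Amendment 4.
3. Change SAP 3.1.4.3 to censor patients without an event at the last disease assessment, as in Protocol 13.4.6.1. DOR then follows.
4. Add one sensitivity analysis that censors these patients at their last disease assessment before the new therapy.

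This concerns the analysis endpoint only and proposes no rule for stopping treatment. The cost is wording in both documents and one extra run, with no change to sample size.

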#### **Radiological Assessment**

Radiological assessments will be performed using MRI scans. The acquisition protocol for MRI (provided as a separate document) will provide further details for scan standardization. All efforts should be made to perform MRI scans according to the corresponding specification in order to ensure that quality of MRI will be standardized among all sites. Consistency of subsequent MRIs should be ensured during all assessments for each patient, with the same technique being used for evaluating lesions. Patients should be imaged on the same MRI scanner for the duration of the study. A 1.5T or 3T scanner must be used for this study. The use of IV contrast should, as long as clinically possible, be kept consistent. The following sequences of the entire brain must be acquired:

- T1 pre-gadolinium
- T2/FLAIR
- T1 post-gadolinium

Target Lesions: Lesions should be measured on the greatest size (bi-dimensional
measurement of the longest cross-sectional diameters) observed either on axial, coronal,
or sagittal slices, and the most representative observed chosen to be followed for
response evaluation (i.e., once selected at baseline, the plane should be maintained
across the study, to allow comparison). If there are multiple contrast- enhancing lesions,
a minimum of two of the largest lesions, and a maximum of five lesions, should be
measured, and the sum of the products of the perpendicular diameters of these lesions
should be determined. Occasionally, the largest lesions may not lend themselves to
reproducible measurements, and the next largest lesions that can be measured
reproducibly should be selected. For patients with recurrent disease who have multiple
lesions of which only one or two are increasing in size, the enlarging lesions should be
considered the target lesions for evaluation of response.
Nontarget Lesions: All other lesions will be considered nontarget lesion requiring

discontinuation of therapy or development of a new contrast-enhancing lesion may occur, even in the setting of stable disease or partial response in the target lesions. These changes would qualify as progression.

Tumor measurements should be made by the same investigator/radiologist for each patient during the study to the extent that this is feasible.

A radiological assessment of complete response (CR) or partial response (PR) requires confirmatory imaging at least 4 weeks after the initial assessment of response was observed. In the event that the radiographic changes are equivocal and it is unclear

whether the patient has stable or progressive disease, treatment should be continued and the patient should be closely observed. If subsequent imaging studies demonstrate that progression has occurred, the date of progression should be the date of the scan at which disease progression was first suspected.

#### **Clinical Status**

Clinical deterioration is defined as a decline in the Karnofsky performance status from 100% or 90% to  $\leq$  70%; a decline of  $\geq$  20% from 80% or less; or a decline from any baseline value to 50% or less, for at least 7 days, unless attributable to comorbid events (e.g., seizures, medication adverse effects, complications of therapy, cerebrovascular events, infection, etc.). Clinical status must be recorded as Improved, Stable, or Worsened.

#### **Corticosteroid Dose**

At the time of each disease assessment, the corticosteroid intake will be compared with corticosteroid intake at the time of the last disease assessment. The changes will be recorded as Increased, Unchanged, or Decreased. Increases or decreases in corticosteroid dose should be clinically justified.

Note: Increases in corticosteroid dose for reasons other than disease control do not need to be taken into consideration when making this comparison.

#### **Overall Disease Assessment**

Based on radiological assessments, clinical status, and corticosteroid use, an overall evaluation of CR, PR, stable disease (SD), or progressive disease (PD) should be made at each disease assessment after baseline according to the RANO criteria (Appendix 2). Progressive disease is defined as any of the following:

- ≥ 25% increase in sum of the products of perpendicular diameters of enhancing lesions (compared with baseline if no decrease or otherwise compared with the smallest recorded sum [nadir] during the study) on stable or increasing doses of corticosteroids
- Significant increase in T2/FLAIR non-enhancing lesions on stable or increasing doses or corticosteroids (compared with baseline or best response after initiation of therapy)
- Appearance of any new lesions
- Clear progression of nonmeasurable lesions
- Definite clinical deterioration not attributable to other causes apart from the tumor, or to decrease in corticosteroid dose

Failure to return for evaluation as a result of death or deteriorating condition
 Note: Increase in corticosteroid dose alone, in the absence of persistent clinical
 deterioration related to tumor, will not be used as a determinant of progression. Patients
 whose corticosteroid dose was increased for new symptoms and signs without
 confirmation of disease progression on neuroimaging do not qualify for disease
 progression and should continue study treatment. If subsequent follow-up imaging
 shows that this increase in corticosteroids was required because of disease progression,
 the date of progression should be the first timepoint at which the increase in

	corticosteroids was necessary.
Patient Reported	Patient reported outcomes (PROs) of disease- and treatment-related symptom severity
Outcomes and Mini-	and symptom interference will be assessed using the MDASI-BT questionnaire.
Mental State	
Examination	The MDASI is a validated and reliable self-report measure that was developed to assess
	symptom sevently and interference [Cleeland 2000; Armstrong 2006].
	Thirteen items ask patients to rate how severe the symptoms were when "at their worst" in the last 24 hours with regard to pain, fatigue, nausea, disturbed sleep, distress, shortness of breath, remembering things, lack of appetite, drowsy, dry mouth, sad, vomiting, and numbness or tingling. An additional six items ask patients to rate how much the symptoms have interfered with six areas of function (general activity, walking, work, mood, relations with other people, and enjoyment of life) in the last 24 hours. The MDASI-BT (see Appendix 3) contains an additional nine items that assess symptoms and concerns specific to primary brain tumor patients (difficulty understanding, difficulty speaking, difficulty concentrating, seizures, weakness, change in appearance, change in vision, change in bowel patterns, irritability), for a total of 28 items.
	Subjects completing 24 cycles of tesevatinib will no longer be required to complete patient reported outcomes and mini-mental state examinations.
Statistical methods	Analysis populations
	Adult patients with recurrent glioblastoma, meeting all inclusion criteria and no exclusion criteria, with availability of paraffin-embedded tumor samples diagnostic of glioblastoma will be enrolled.
	Two subgroups of patients are defined as having: EGFRvIII pos and EGFR amplification pos tumors.
	Primary and secondary efficacy analyses will include all patients who were included in the study. The same analysis methods for the primary and secondary analyses will be applied to both the ITT population and the EGFRvIII pos and EGFR gene amplification pos population.
	Safety analyses will include all patients who enrolled and received at least one dose of study treatment (the safety population).
	All patients who take at least one dose of tesevatinib will be evaluable for safety and efficacy assessments.
	Patients who do not complete the study, for whatever reason, will have all available data (up until the time of termination related to the reason they were terminated) included in the analysis.
	For statistical purposes, completion of the study will be defined as six months after the last patient starts study treatment.
	The plasma concentration analysis population will consist of all patients who receive at least one dose of tesevatinib, and who have at least one sample analyzed for plasma concentrations.

